Appendix H. Shipping Information for HLA Testing

HLA specimen collection kit containing 3 ten ml EDTA purple top tubes provided by Roswell Park.

Collect should occur at baseline if HLA typing has not already performed.

Specimens should be shipped via Prime Time Courier, ambient on the same day of collection, with enclosed Immco specimen requisition. This will be handled by Roswell Park Lab medicine department and shipped to:

Immco Diagnostics
[name]
[name]

Appendix I. Assessment of T cell Responses

CD4⁺ and CD8⁺ cells will be enriched from PBMCs by magnetic cell sorting using miniMACS (Miltenyi Biotec Inc., Bergisch Gladbach, Germany) and stimulated with irradiated autologous APCs in the presence of NY-ESO-1 peptide pool (each 2 µM; NeoMPS Inc., San Diego, CA), rhIL-2 (10 IU/mL), and rhIL-7 (10 ng/mL). At Day 8, cultures will be tested for intracellular IFN-γ secretion after stimulation, during 4 hours, and in the absence or presence of the peptide pool or of individual peptides. Response will be considered significant if the frequency of T cells detected in at least one post vaccine sample exceeded by 3-fold that found in the baseline sample.

For ex vivo assessments, cryopreserved total PBMCs will be thawed, rested overnight, and stimulated for 7 hours in the absence or presence of the NY-ESO-1 peptide pool. Brefeldin A will be added 2 hours after the beginning of the incubation. At the end of the incubation, cells will be stained with antibodies directed against surface markers (CD3, CD4, CD8, CD45RA, and CCR7), fixed, permeabilized, and stained with cytokine-specific antibodies.

1. INFORMED CONSENT

- Informed consent must be obtained by the **site Investigator** from any subjects wishing to participate, **prior to any procedures or change in treatment**.
- An informed consent template is provided by Roswell Park and can be amended to reflect institutional requirements.
- All consent changes **must** be reviewed by Roswell Park Network Office prior to submission to the site IRB.
- The informed consent must be IRB approved.
- Always check that the most up to date version of the IRB approved consent is being used.
- Within 5 business days, notify the Roswell Park Network Office of all participant withdrawals or consent to limited study participation and appropriately document the discontinuation and the reason (s) why.

2. SUBJECT REGISTRATION

The subject completes the **Gender, Race, and Ethnicity Form** and this is placed in the study binder.

Roswell Park does not grant exceptions to eligibility criteria.

Phase 2 Protocol Registration Instructions

The **Subject Enrollment Log** must be faxed or emailed to the Roswell Park Network Office within 24 hours of the date the subject is consented. Once the Investigator has determined that eligibility has been met, complete the **Subject Registration Form and fax or email** it to the Roswell Park Network Monitor at [contact].

3. STUDY DEVIATIONS

- If a deviation has occurred to eliminate hazard, this must be reported to the Roswell Park Network, site IRB and any other regulatory authority involved in the trial.
- All study deviation will be recorded on the **Study Deviation Log**.
- Subjects inadvertently enrolled with significant deviation(s) from the study-specified criteria will be removed from the study.

4. STUDY DOCUMENTATION

- Study documents must be filled out completely and correctly. Ditto marks are not allowed.
- If an entry has been documented in error put a single line through the entry and initial and date the change. The Roswell Park Network Monitor must be able to read what has been deleted.
 - Do **NOT** use white-out, magic marker, scratch-outs.
 - Do **NOT** erase entries.
- Use only black ink for documentation on the accountability form and any other study forms.

5. DRUG ACCOUNTABILITY

Drug accountability must be strictly maintained.

- Responsibility rests solely with the Investigator but can be delegated as appropriate (e.g., to pharmacy personnel).
- A drug accountability record form (DARF) will record quantities of study drug received, dispensed to subjects and wasted, lot number, date dispensed, subject ID number and initials, quantity returned, balance remaining, manufacturer, expiration date, and the initials of the person dispensing the medication.
- Study drug supply will only be used in accordance with the IRB approved study.
- Drug accountability forms are protocol and agent specific, they are study source documents and will be used to verify compliance with the study.

- An inventory count must be performed with each transaction. Any discrepancies shall be documented and explained.
- Drug accountability forms must be stored with study related documents.
- Each medication provided for this study and each dosage form and strength must have its own DARF.
- Dispensing the wrong study supply is considered a **medication error**.
 - **NEVER** replace investigational agents with commercial product.
 - Do **NOT** “transfer”, “borrow” or “replace” supplies between studies.

6. SERIOUS ADVERSE EVENT REPORTING

The site Investigator or designated research personnel will report all SAEs, whether related or unrelated to the investigational agent(s) to the **IRB in accordance with their local institutional guidelines**. The site will notify the Roswell Park Network Monitor within 1 business day of being made aware of the SAE. A preliminary written report must follow within 24 hours (1 business day) of the first notification using the following forms:

- Roswell Park SAE report form
- MedWatch 3500A

Investigators MUST report (within 1 business day), upon becoming aware, to Incyte, Sentrx, or Celldex ANY SAEs, whether or not they are considered related to the investigational agent(s)/intervention.

SentrX
[name]
[name]
[name]

SAE Facsimile Number: Sentrx: [contact]

SentrX Helpdesk Phone (Helpdesk support available 8am – 8 pm EST):

[contact] (toll free in US)
[contact] Ext: 250

Incyte Pharmacovigilance
[name]
[name]
[contact]

All SAE reports are to be sent via e-mail to: [contact]

Celldex Therapeutics, Inc.
SAE Reporting
[contact]

E-mail: [contact]

A complete follow-up report must be sent to the Roswell Park Network Monitor within 10 working days.

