6.3.1 Definition of Dose-Limiting Toxicity

Patients who do not complete the study through Day 29 for reasons other than dose limiting toxicities (DLTs) will be replaced. All patients will be included in the analysis results.

All AEs (as defined in **Section 9**) will be graded according to the NCI-CTCAE scale Version 4.0. Patients who experience a DLT will not receive any additional treatment (i.e., will be removed from the study and followed until resolution of their toxicity) and will not receive continued treatment even at a reduced dosage of the INCB024360 product. Patients with dose limiting toxicities requiring drug discontinuation (specified below) will be removed from the study (see exception for hypersensitivity reaction). The DLT period will be defined as 28 days after the first dose of vaccine. Late developing toxicities, occurring between Day 29 and Day 183 will be monitored throughout the study and according to the schedule of procedures and observations. Patients may be withdrawn from study even if DLT is due to INCB024360 or sirolimus alone. Safety monitoring will include careful assessment and appropriate reporting of AEs, as well as the construction and implementation of a data and safety-monitoring plan (Auditing, Monitoring, and Inspecting). Medical monitoring will include a regular assessment of the number and type of SAEs. Refer to the stopping rules for this study in **Section 6.3.2**. Any event(s) that might appear to trigger a treatment discontinuation rule or trial stopping rule will be discussed with the FDA review team. For phase IIb dose reductions for INCB024360 will be allowed (see section 6.3)

Management and dose modifications associated with AEs are outlined in **Section 6.3**. Refer to **Section 11** for statistical considerations and additional decision rules.

These events should be deemed to be possibly, probably or definitely related to study drugs. DLT criteria will be defined as any Grade 3 or higher treatment-related (i.e. definitely, probably, or possibly related) toxicity that occurs during the DLT evaluation period, including:

- Febrile neutropenia with standard of care treatment for ≥ 7 days. Growth factors may be used according to American Society of Clinical Oncology guidelines.
- Platelets $\leq 50 \times 10^9/L$
- Grade 3 or greater non-hematologic toxicity
- New onset pulmonary hypertension, interstitial pneumonitis or, CNS bleeding
- Serum bilirubin $> 3.0 \text{ mg/dL}$

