6.3.2 Management of Delayed Events

Late-developing toxicities, occurring between Day 29 and Day 143 will be monitored throughout the study and according to the schedule of procedures and observations.

Study Stopping Rules

Any Grade 4 event will trigger a study pause for data review prior to further enrollment. In addition, the following stopping rule for treatment-related SAEs will be used:

- Accrual to study will be suspended to allow protocol review with institutional IRB, the Early Phase Clinical Trials (EPCT) Committee, and the FDA review team if any of the following occurs among patients who receive experimental agents:
 - Any treatment-related death, judged to be possibly, probably, or definitely related to INCB024360 or DEC205mAb-NY-ESO-1 fusion protein (CDX-1401) given with adjuvant poly-ICLC.
 - Exploratory cohort at Roswell Park ONLY: Any treatment-related death, judged to be possibly, probably, or definitely related to sirolimus or DEC205mAb-NY-ESO-1 fusion protein (CDX-1401) given with adjuvant poly-ICLC.
 - Grade 4 events considered to be possibly, probably, or definitely related to the experimental agents.

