9.2 Serious Adverse Events

9.2.1 Definition

A serious adverse event (SAE) is any adverse event (experience) that in the opinion of either the investigator or sponsor results in **ANY** of the following:

- Death.
- A life-threatening adverse event (experience). Any AE that places a patient in the view of the Investigator or sponsor, at immediate risk of death from the reaction as it occurred. It does **NOT** include an AE that, had it occurred in a more severe form, might have caused death.
- Inpatient hospitalization or prolongation of existing hospitalization (for > 24 hours).
- A persistent or significant incapacity or substantial disruption of the ability to conduct normal life functions.

- A congenital anomaly or birth defect.
- Important Medical Event (IME) that, based upon medical judgment, may jeopardize the patient and may require medical or surgical intervention to prevent one of the outcomes listed above.

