9.3 Unanticipated Problems

9.3.1 Definition

An Unanticipated Problem (UP) is any incident, experience, or outcome that meets all of the following criteria:

- Unexpected (in terms of nature, severity, or frequency) given:
 - a) The research procedures that are described in the study-related documents, including study deviations, as well as issues related to compromise of patient privacy or confidentiality of data.
 - b) The characteristics of the patient population being studied.
- Related or possibly related to participation in the research (possibly related means there is a reasonable possibility that the incident, experience, or outcome may have been caused by the procedures involved in the research).
- Suggests that the research places patients or others at a greater risk of harm (including physical, psychological, economic, or social harm) than was previously known or recognized and if in relation to an AE is also deemed **Serious** per **Section 9.2**.

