14 STUDY RESPONSIBILITIES

14.1 Data Collection

Data entry into the database is to be completed in a timely fashion (approximately within 28 days) after the patient's clinic visit. If an AE is considered serious it is captured on both the Adverse Event page and the Serious Adverse Event Form, which is handled in an expedited fashion.

Data management activities will be performed using EXPeRT. EXPeRT is a suite of software tools that enables the collection, cleaning and viewing of clinical trial data. CRS data management will design the study-specific database and facilitate its development by the EXPeRT Information Technology team. Once the database design is approved by the Investigator, Statistician, and Clinical Research Coordinator, the database will be put into production and data entry can begin. Data can be entered and changed only by those with the rights to do so into the eCRFs. EXPeRT is compliant with all relevant technical aspects of relevant GCP guidelines.

- The system can generate accurate copies of stored data and audit trail information in human readable form.
- System access is limited to authorized individuals through the controlled assignment of unique ID and password combinations.

- The system is designed to periodically force users to change their passwords and verifies that user ID and password combinations remain unique.
- The system automatically generates a permanent time-stamped audit trail of all user interactions.

When data entry is complete, data management will review the data and will query any missing, incomplete, or invalid data points for resolution by the CRC and Investigator. Once all queries have been resolved, the data can be released to the statistician for analysis.

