7. UNANTICIPATED PROBLEM REPORTING

An unanticipated problem (UP) is any incident, experience, or outcome that meets **all** of the criteria in **Section 9.3**

For all adverse events occurring that are unanticipated and related or possibly related to the research drug, biologic or intervention, the participating physician or delegated research staff from each site will notify **their local IRB in accordance with their local institutional guidelines**. The site must also notify the Roswell Park Network Monitor within 24 hours of being made aware of the Unanticipated Problem by completing the **Roswell Park Reportable New Information Form** and faxing or emailing it to the Roswell Park Network Monitor.

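### The study pause is triggered by any Grade 4 event, but the network site has a reporting deadline only for serious events and unanticipated problems, so a non-serious Grade 4 event has no stated prompt route to the other site

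*Combined protocol and SAP*

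**What the plan says.** Section 6.3.2 sets the pause: "Any Grade 4 event will trigger a study pause for data review prior to further enrollment". It has no limit by seriousness, attribution, arm or site. The same section also suspends accrual, pending wider review, for "Grade 4 events considered to be possibly, probably, or definitely related to the experimental agents". Both rules turn on grade.

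The timed reports turn on seriousness.

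- Appendix J, section 6 (SAEs): "The site will notify the Roswell Park Network Monitor within 1 business day of being made aware of the SAE".
- Appendix J, section 7 (unanticipated problems): "The site must also notify the Roswell Park Network Monitor within 24 hours of being made aware of the Unanticipated Problem". Section 9.3.1 requires an unanticipated problem to suggest greater risk than was previously "known or recognized and if in relation to an AE is also deemed" serious under 9.2.
- Sections 9.2.2 and 9.3.3 set deadlines for notifying the drug suppliers, again for SAEs.
- Section 14.1: "Data entry into the database is to be completed in a timely fashion (approximately within 28 days" of the clinic visit). Only serious events are expedited.

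Table 8 lists Grade 4 events of every attribution among the routine Phase IIb adverse events. The text below it gives a collection window but no deadline for telling Roswell Park.

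**The concern.** Grade and seriousness are different scales. Section 9.2.1 defines seriousness by outcome (for example, being "at immediate risk of death from the reaction as it occurred", or hospitalisation) or by a medical judgment that the event is important. Grade is not a criterion. A Grade 4 laboratory abnormality in a patient who is otherwise well and not admitted need not qualify.

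If such an event occurs at the University of Pittsburgh, the site can follow every timed reporting rule and Roswell Park may still not hear of it for weeks. Roswell Park could then go on registering patients when 6.3.2 says enrolment is paused. What is at stake is whether an automatic safety rule takes effect at both randomising sites when it should.

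**Working it through.** **Step 1. Which routes carry a non-serious Grade 4 event from the network site?**

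| Route | Carries it? | Deadline for the site |
|---|---|---|
| SAE notice (Appendix J section 6; 9.2.2) | No, serious only | 1 business day |
| Unanticipated problem (Appendix J section 7 with 9.3.1) | No, an adverse event must be serious | 24 hours |
| Routine adverse event (Table 8) with data entry (14.1) | Yes | None for notification; about 28 days for entry |
| Weekly safety evaluation (11.5) | Possibly | None; no network-site data feed described |
| Contact with the principal investigator for attribution (6.3) | Only for INCB024360 toxicity | None; not linked to the pause |
| FDA discussion of events that may meet a stopping rule (6.3.1) | Yes | None |
| DSMC review (10; 11.5) | Eventually | Annual |

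Appendix J section 7, read by its own words without 9.3.1, would still cover only unanticipated events at least possibly related to treatment. Expected or unrelated Grade 4 events would stay outside it. The medical monitoring in 6.3.1 is also framed by seriousness: "Medical monitoring will include a regular assessment of the number and type of SAEs". No route combines coverage of this event with a prompt deadline.

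**Step 2. Possible delay, counted from the clinic visit.**

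- Weekly review draws current site data: up to about 7 days.
- First seen in the database: up to about 28 days.
- Database entry, then the next weekly review: 28 + 7 = 35 days.

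Time between onset and the visit is left out, because a notification rule cannot shorten it.

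**Step 3. Enrolment during the delay.**

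Inputs are 50 Phase IIb patients and about 8 years of accrual (3.1.1). I assume even accrual and count both sites.

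Expected enrolments = days × 50 / (8 × 365.25) = days × 50 / 2,922.

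- 28 days: 1,400 / 2,922 = 0.48. If arrivals are Poisson, the chance of at least one is 1 − exp(−0.48) = 0.38.
- 7 days: 350 / 2,922 = 0.12.
- 1 day, as under the fix: 50 / 2,922 = 0.02.

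The site that saw the event already knows of it, so the relevant number is the share at the other site, which is smaller. The split between sites is not given. The 8 years also spans Phase I, so the rate while Phase IIb is open could be somewhat higher.

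The sample size section (11.1.1) instead assumes 9 months of accrual, which would give 28 × 50 / (9 × 30.4375) = 5.1 patients. That is an input to the power simulation and conflicts with the 8 years stated in the synopsis, 3.1.1 and 6.6. I do not use it as the estimate.

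**The case against.** The case against has real force on size, less on substance.

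- **Other escalation exists.** Section 11.5 describes weekly evaluation of adverse events and laboratory values, 6.3 asks sites to contact the principal investigator, and 6.3.1 requires FDA discussion of any event that may meet a stopping rule, serious or not. A data and safety-monitoring plan is also mentioned but is not in the documents. This stands as a reason not to treat 28 days as the expected delay. It does not supply a site deadline.
- **The rule already binds the site that sees the event.** A reader might infer that the pause cannot work at Pittsburgh. The documents do not support that: continuing to enrol there would breach 6.3.2. The exposure is at the site that has not been told.
- **Treated patients.** A reader might infer that patients already on treatment should have been held too. Section 6.3.2 speaks of further enrolment and does not expressly halt dosing, so that harm cannot be claimed.
- **The affected set is narrow.** Under 9.1.1.3 a laboratory abnormality is recorded as an adverse event only if it is clinically significant and needs active management, and an investigator might call many of those important medical events. Section 1.6.2.4 names hypokalemia among the most common Grade 3 or 4 events, and reports Grade 3 or 4 AST and ALT elevations in 5 of 7 patients, only one with a bilirubin rise (Grade 1). But it pools the two grades, and the 5 of 7 received ipilimumab rather than this vaccine. The set is small but not empty, and an automatic pause should not depend on a discretionary seriousness call.
- **Text not seen.** A short stretch just before item 1 of Appendix J is absent from the copy reviewed. The numbered items 1 to 8 are present, so a missing deadline there is unlikely but not excluded.

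**Conclusion.** The mismatch holds. The pause is triggered by grade, every prompt report from the network site depends on seriousness, and no provision gives a site deadline for a non-serious Grade 4 event. Sites following the reporting rules exactly can leave the other site enrolling when 6.3.2 says enrolment is paused.

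The size is modest. The delay ranges from about 7 days to 28 days or more; 28 days is a data-entry allowance, not a forecast. Expected Phase IIb enrolment in 28 days is about 0.5 patients across both sites and less at the uninformed site, assuming even accrual over 8 years. This is the number exposed once such an event has occurred. It is not an unconditional expectation, because the probability of the event is unknown. A reader might take the 9-month accrual and conclude that about 5 patients would enrol. The documents do not support that as an operational figure, and it also counts the site that already knows.

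The sponsor should make the change because a safety rule lacks a link that is simple to supply, not because large exposure has been shown.

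**What to change.** In Appendix J section 6 and in 9.2.2, require the site to notify both the Network Monitor and the Roswell Park principal investigator of any Grade 4 event, serious or not and whatever its attribution, within 1 business day of becoming aware of it.

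State in the same place that new registrations at both sites are held until the 6.3.2 data review is documented. The hold must name Roswell Park expressly: Appendix J section 2 routes network-site registration forms through the Network Monitor, and nothing shows that Roswell Park's own registrations pass that way. Add a cross-reference from 6.3.2 so that the trigger and the notice stay aligned.

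The pause rule itself is unchanged. The cost is a sentence or two in each place and a few extra e-mails. No new data are collected.

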7. UNANTICIPATED PROBLEM REPORTING

An unanticipated problem (UP) is any incident, experience, or outcome that meets **all** of the criteria in **Section 9.3**

For all adverse events occurring that are unanticipated and related or possibly related to the research drug, biologic or intervention, the participating physician or delegated research staff from each site will notify **their local IRB in accordance with their local institutional guidelines**. The site must also notify the Roswell Park Network Monitor within 24 hours of being made aware of the Unanticipated Problem by completing the **Roswell Park Reportable New Information Form** and faxing or emailing it to the Roswell Park Network Monitor.

